Analyses will include participants who drop out before completion of the 12-week intervention period by way of multiple imputation. This intention to treat approach will investigate factors that may affect compliance and difficulty with exercise training, including soreness and medical comorbidity. If the pattern of missing data is missing completely at random, or simply at random, our multiple imputation should eliminate bias due to loss to follow-up. Because the participants will be recruited from clinic-based VA cohorts, we will be able to obtain clinical data from participants who drop out of the study, but remain in clinical care, to determine if drop-out was related to medical conditions that may influence outcomes. Thus, we will be able to estimate bias introduced by loss to follow-up. If there is sufficient information, we may be able to model the drop-out process and adjust our analyses for loss to follow-up even if the missing data pattern is non-ignorable. If 36 training sessions cannot be completed in 12 weeks, then total training time will be tracked, and incorporated into the data analysis.

DNA Methylation (AIM 3): We will examine the change of methylation levels after 12 weeks for each candidate marker using ANOVA models. To examine epigenetic association with each outcome, we will fit the linear regression model as follows: where Y_i is the quantitative outcome measurement, Z_i is the vector of covariates including age, race, smoking status and leukocyte proportions, and E_i is the candidate epigenetic marker. ANCOVA will be used to test for between group difference by time (pre/post exercise). The candidate epigenetic markers will involve individual CpG sites previously identified and discussed in detail section D4c. We will extend this linear regression model to account for batch/chip effects and

longitudinal measures using a linear mixed model. We will adjust the significance threshold for multiple testing using Bonferroni correction ($p < 0.05 / \text{number of tests}$).

Sample Size Estimates:

AIM 1. Paired t-test was used to test for a mean change given a range of correlation between pre and post values with assumptions of $\alpha = 0.05$ and 80% power. (Mean (SD) values for the VO_2peak are from our current high-intensity AEX + RT trial in HIV+ Veterans (Table 3). Data for 2-minute step test are from our VTEL Gerofit exercise program (C3). Values for chair stands are results from a 10-week RT in older men.⁴⁶ We will have adequate

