3 STUDY METHODS

3.1 Study Design

This study is a multi-site exercise intervention for Veterans receiving care at the Atlanta and Baltimore VAMCs that will randomize approximately 80 participants (40 per site) at these VAMCs, herein referred as enrollment sites. The intervention is 12-weeks of high-intensity functional circuit exercise performed 3 times weekly in a supervised group setting. Exercise training will be led by an exercise physiologist at the Salem VAMC (coordinating site) and broadcast to the enrollment sites. HIV-infected Veterans 50 years of age and older will be enrolled at the Atlanta and Baltimore VAMCs. Eligible participants will be randomized to exercise training (N=40) or control (N=40) groups. All participants will undergo baseline testing and follow up testing after 12 weeks at their respective enrollment site. Participants in the Control Group will be instructed to maintain their baseline sedentary lifestyle (as defined in eligibility criteria) during the 12-week intervention period. After follow-up testing is complete, participants in the control group will have the option of completing 12-week exercise training (delayed entry exercise) which will be a combined home and center-based exercise program. Pre-post exercise testing will be conducted in these participants to gauge individual progress and provide individual feedback that is a benefit of study participation, but these results will not be part of the randomized trial analyses.

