Feasibility of the project is supported by investigators with a track record of collaboration and the existing infrastructure including experience staff, well-defined population, and available exercise, VTEL, and lab equipment. Based on prior exercise trials we have conducted in this population, we expect a 33% eligibility failure rate and a 30% attrition rate. Due to the COVID hold in 2019-2000, first study year, no participant activity occurred and a 1-year cost-extension has been awarded which will allow for completion of 40 participants per site to complete the exercise trial within the project period (Table 5).

Table 5	Y 2				Y 3				Y 4				Y 5				total
	1	2	3	4													
Quarter	1	2	3	4	1	2	3	4	1	2	3	4	1	2	3	4	
Completers	2	6	6	6	6	6	6	6	6	6	6	6	6	4	2		80
AVAMC	1	3	3	3	3	3	3	3	3	3	3	3	3	2	1		40
BVAMC	1	3	3	3	3	3	3	3	3	3	3	3	3	2	1		40

Eligibility

HIV+ adult men and women of all races and ethnicities who are 50 years of age and older will be eligible. Eligibility criteria are based on our exercise research in older HIV+ adults and American College of Sports Medicine guidelines and are designed to minimize attrition, maximize safety, and limit confounding

factors. Of note, smoking is not an exclusion criterion since approximately 70% of the otherwise eligible HIV+ Veterans are smokers, and if excluded would decrease the study's generalizability.

Inclusion Criteria: Participants will be on antiretroviral therapy with HIV viral suppression because HIV viremia affects DNA methylation and DNA age. Only sedentary adults will be eligible (not engaging in structured activity for exercise ($\geq 1/\text{week}$)).

Exclusion Criteria: Specific eligibility criteria are listed in Table 6 below and include objective cut-off limits designed to maximize safety and minimize attrition but not prohibitively limit enrollment and maintain generalizability. Eligibility will be determined by information collected by a clinician study investigator during the eligibility visit which occurs after informed consent is obtained. The eligibility visit includes history and physical exam (H&P), review of the electronic medical record, and resting ECG. The following eligibility checklist was used for IRB submission at the enrollment sites:

Table 6. Eligibility Checklist		
*based on date of H&P		
Inclusion Criteria		
Yes	No	
		Veteran living with HIV and under care at VAMC
		50 years of age and older
		Stable antiretroviral therapy (ART) (same ARV medications within 3 months)

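### Relating drop-out to conditions in the clinical record does not let the trial estimate bias in outcomes measured only at study visits, and no sensitivity analysis for non-ignorable drop-out is fixed

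*Combined protocol and SAP*

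**What the plan says.** Section 2.3.e (Statistical Plan) includes drop-outs through multiple imputation. It says that if data are missing completely at random or at random, "our multiple imputation should eliminate bias due to loss to follow-up".

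It then turns to clinical data on "participants who drop out of the study, but remain in clinical care", to be used "to determine if drop-out was related to medical conditions that may influence outcomes". The next sentence draws the conclusion: "Thus, we will be able to estimate bias introduced by loss to follow-up". The last step is conditional: "If there is sufficient information, we may be able to model the drop-out process" and adjust for loss "even if the missing data pattern is non-ignorable".

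No test, relevant difference, drop-out model, range of assumptions or sensitivity analysis is named. The text does not say which variables enter the imputation.

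On scale, section 3.1 states: "Eligible participants will be randomized to exercise training (N=40) or control (N=40) groups". Section 3.3.a (Enrollment and Completion Targets) states: "we expect a 33% eligibility failure rate and a 30% attrition rate".

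**The concern.** The check and the conclusion concern different quantities. The check relates drop-out to recorded conditions. Outcome bias depends on how far the drop-outs' unseen 12-week values lie from the values imputed for them. For VO2peak, DXA, the function tests and DNAm Age, the procedures in section 3.3.b are study-visit measurements, so the clinical record does not hold the missing values.

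Neither result of the check closes the gap. If drop-out is related to recorded conditions, that is a missing-at-random pattern, which imputation can handle provided those conditions are in the model. If it is not related, little has been learned about drop-out that depends on the response itself.

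The quoted conclusion is the plan's only firm assurance beyond the missing-at-random case. The training is demanding, participants know their arm, and section 2.3.e itself expects difficulty with training, including soreness. It is therefore plausible that poor responders leave the exercise arm more often. That would make the imputed intention-to-treat result too favourable to exercise.

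**Working it through.** **The plan's own attrition figure.** No power or precision is stated for the drop-out check. The nearest figure is the DNAm Age sample size of 29 at correlation 0.3, said to be adequate with 28% attrition.

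- SD of change = √(10.8² + 10² − 2 × 0.3 × 10.8 × 10) = √151.84 = 12.32.
- Standardised change = (68.7 − 62)/12.32 = 0.544.
- A two-sided paired t-test at 0.05 first reaches 80% power at n = 29, as stated. 40 × 0.72 = 28.8, about 29.

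So the figure reproduces, but attrition enters it only as lost numbers and not as possible bias.

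**What is missing and what the record could supply.**

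| Source in the plan | What it gives for a drop-out |
|---|---|
| Clinical record (2.3.e) | Conditions, if still in care |
| Clinical laboratory values (3.3.b, VACS Index) | Part of one secondary frailty measure |
| Aggregate reasons for loss (2.3.e) | Description of why people left |
| Training logs and heart-rate data (3.2.a) | Training up to drop-out, exercise arm only |
| Study-visit testing (3.3.b) | VO2peak, DXA, function, DNAm Age: absent |

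**Illustration of drop-out driven by response (assumed model).** 4,000 simulated exercise arms of 40.

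- Follow-up Y = 0.5X + √0.75 U, where X is baseline and U the unseen response; Y has SD 1.
- Log-odds of drop-out = a − slope × U, with a set to give 30% drop-out.
- A recorded condition has absolute correlation ρ with U, worse condition going with poorer response.
- Missing Y is imputed by regression on baseline, with the condition added in the second and third rows.
- The check is a two-sided 5% t-test of the condition, drop-outs against completers within the arm.

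| ρ | Check significant (slope 0.5 / 1.0 / 1.5) | Imputed mean too favourable, SD |
|---|---|---|
| 0 | about 5% throughout | 0.12 / 0.22 / 0.28 |
| 0.3, condition in model | 7% / 11% / 15% | 0.11 / 0.20 / 0.26 |
| 0.5, condition in model | 10% / 23% / 35% | 0.09 / 0.17 / 0.23 |

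Pooling both arms, with control drop-out unrelated to anything, lowers the correlated-case rates to about 6% to 21%.

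A second model estimated the group difference directly, with 40 per arm and adjustment for the condition. It gave bias of 0.12, 0.25 and 0.35 SD for the same slopes when drop-out followed the unseen response. When drop-out instead followed the recorded condition (mean difference 0.47 to 0.52 SD), the check was significant in 49% to 57% of trials and adjustment left about zero bias. The check is thus most likely to react in the case that imputation already handles.

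**Power of such a comparison, if one were tested.** Two-sample t-test, two-sided 0.05. Randomising 80 with 30% loss gives 24 drop-outs and 56 completers. If 80 means completers (Table 5), 80/0.70 = 114 randomised and 34 drop-outs.

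| Drop-outs v completers | Power at assumed 0.5 SD |
|---|---|
| 24 v 56 | 53% |
| 34 v 80 | 68% |
| 12 v 28 (exercise arm only) | 29% |

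For 24 v 56, power runs from 23% at 0.3 SD to 90% at 0.8 SD.

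**Size against the planned effects**, using the follow-up SDs in the sample-size table. For VO2peak, 0.12 to 0.28 SD is 0.12 × 0.14 = 0.02 to 0.28 × 0.14 = 0.04 L/min, against an assumed change of 2.46 − 2.17 = 0.29. For DNAm Age it is 0.12 × 10 = 1.2 to 0.28 × 10 = 2.8 years, against 6.7.

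**The case against.** The plan is vague rather than unaware. It limits its claim for imputation to missing-at-random data, names the non-ignorable case, collects reasons for loss, will investigate factors affecting compliance, and keeps session-level training data. Nothing says that clinical variables are left out of the imputation. All of that stands, and it makes the repair easy. But these sources describe drop-out; they do not estimate outcome bias.

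Three stronger readings are tempting, and the documents do not support them.

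- A reader might infer that a non-significant comparison will be taken as proof of no bias. The plan names no test and states no such rule. This is a risk in the wording, not a planned step.
- A reader might infer that the check misses about half of relevant differences. That holds only for an assumed 0.5 SD with 24 v 56. Over 0.3 to 0.8 SD the miss rate runs from 77% to 10%, and at 0.5 SD it is 32% for 34 v 80.
- A reader might infer that the check is silent about response-driven drop-out and that records can recover no outcome. The rate near 5% is built in when condition and response are unrelated. The plan looks at conditions that may influence outcomes, so some weak sensitivity is likely, and the VACS Index is partly recoverable.

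It is also fair that a bias of this size would not overturn the VO2peak, step-test or chair-stand changes if they are as large as assumed: 0.29/0.13 = 2.2, 19/18 = 1.1 and 7.6/5.4 = 1.4 baseline SD. DNAm Age, at 6.7/10.8 = 0.6 SD, is more exposed.

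**Conclusion.** The concern holds in a limited form. For outcomes measured only at study visits, the step from recorded conditions to an estimate of bias does not follow, and the sentence after it commits to no method. This rests on the text and not on the simulation.

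Under the stated assumptions, response-driven drop-out would leave the imputed exercise-arm mean too favourable by about 0.12 to 0.28 SD, or 0.09 to 0.26 SD with a correlated condition in the imputation model. The within-arm comparison would be significant in about 5% to 35% of trials. The slopes, correlations and 0.5 SD difference are assumptions; the 30% attrition and 40 per arm are the plan's. Whether drop-out will in fact depend on response is unknown, which is why the range of assumptions should be fixed before results are seen.

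**What to change.** In section 2.3.e:

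1. Replace the sentence claiming that bias can be estimated. Say that the comparison describes recorded differences between drop-outs and completers, reported with 95% confidence intervals and not as a test of ignorability.
2. State that clinical-record variables enter the multiple imputation as auxiliary variables whatever the comparison shows, with available training data in the exercise arm.
3. Replace the conditional sentence on modelling drop-out with a pre-specified delta-adjusted imputation. Shift imputed values unfavourably in the exercise arm over a stated range, for example 0 to 1 SD, and vary the control-arm shift as well. Report the shift at which each between-group conclusion changes.
4. Note the VACS Index separately, since clinical laboratory values may supply part of it for drop-outs in care.

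The cost is SAP wording and a few re-runs of the planned imputation, with no new data. The downside is that the result may look less robust.

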Treadmill Test	Exercise Capacity	Aerobic capacity (VO ₂ peak)
		O ₂ pulse
		Anaerobic Threshold (AT)
DXA	Body Composition	Body fat
		Appendicular skeletal mass index (ASMI):
		Bone density
Functional performance	Strength and endurance	Chair stand
		Arm curve
		2-minute step test
Frailty		Fried Frailty Phenotype
		VACS Index
Blood Sample	Biomarker of Aging	DNAm Age ²⁰
	DNA Methylation (DNAm) of Candidate Genes	Inflammation-related genes: NFKB2 ⁵⁶ ; ASC ⁵⁷ ; 5 CpG sites in genes related to CRP ^{37,58}
		Exercise-related genes: GHRH and FGF1 ⁴³ ; Epidermal growth factor (EGF) ⁴⁸
	Biomarkers of Inflammation	e.g., IL-6, IL-18, high-sensitivity CRP ^{38-41,43}
Survey	Health-related QoL	WHOQOL-HIV ⁵⁹
	Social Support	Exercise Social Provisions Scale ⁶⁰
	Exercise Barriers	Barriers-Specific Efficacy Questionnaire ⁶¹
	System Usability	System Usability Scale (SUS) ⁶²
Garmin Tracker*	Physical Activity	Step counts
		MVPA minutes
		Sedentary time

*Delayed exercise group only; MVPA, moderate vigorous physical activity

Treadmill Testing: Participants will be asked to exercise to voluntary exhaustion during a graded treadmill test using a modified Bruce protocol.⁶³ After a resting 12-lead electrocardiogram is completed and reviewed by the study physician, participants will be asked to exercise to voluntary exhaustion during a treadmill test using a modified Bruce protocol. A final report on the test results will be made by a

cardiologist. If abnormal findings are seen on the test, the participant will be referred to their primary care physician. The visit for the exercise treadmill test will take about 45-60 minutes and will take place in the Baltimore and Atlanta VAMCs.

Oxygen (O_2) consumption, CO_2 production, and minute ventilation will be measured breath-by-breath using a metabolic cart and the following data will be collected:

VO_2 peak. Rationale: O_2 consumption at peak exercise effort, VO_2 peak, is used as the standard measure of aerobic capacity in sedentary adults since the majority are not able to reach maximal aerobic capacity defined as a plateau in O_2 consumption.⁶⁴ Method: VO_2 peak will be the average of the final 30 second values of O_2 consumption at peak exercise.

O_2 Pulse. Rationale: Oxygen pulse is a measure of the efficiency of O_2 delivered or consumed. Method: O_2 pulse will be calculated as the milliliters of O_2 consumed per heartbeat (VO_2/HR).

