Inflammatory Biomarkers: Testing of inflammatory biomarkers will occur at each respective enrollment site using the same kits since procedures are very standardized. We appreciate that change in plasma levels of cytokines can vary greatly between and within individuals. Our analysis plan takes this point into consideration by including change in cytokines as an independent variable in models of the primary and secondary outcomes. Changes in plasma levels will be calculated pre/post intervention and will be tested for association with changes in outcomes as well as between group differences.

DNA Methylation Assay: Samples will be tested for DNA methylation in the laboratory of [name] in Atlanta using established methods as previously described.^{23,58,78} Samples from Baltimore participants will be shipped directly to [name] lab. In sum, [name] will conduct a comprehensive interrogation of epigenome-wide CpG sites using the Illumina Infinium Methylation EPIC (850K) BeadChip. The 850K chip covers 99% of the NCBI Reference Sequence (RefSeq) genes, with sites covering the promoter, untranslated regions, and gene body, >95% of CpG islands, enhancer regions from FANTOM5 and ENCODE, as well as differentially methylated sites across tissue types. The EZ DNA Methylation Kit (Zymo Research, Orange CA) will be used to bisulfite-convert 0.5 µg of gDNA per sample. Bisulfite-converted DNA samples will be whole-genome amplified, enzymatically fragmented, and purified. Samples will be hybridized to the array. The array will then be fluorescently stained, scanned, and assessed for fluorescence intensities to quantify the methylation levels of each DNAm site.

Blood Banking: Blood sampling will include additional volume for future testing related to cardiometabolic disease and aging. These samples will be stored at the Atlanta and Baltimore VAMCs.

Clinical Data: Medical history and clinical laboratory values will be collected at the eligibility visit by a research clinician. Data will include comorbid conditions, medication use, CD4 cell count and HIV-1 PCR level, and other clinical labs included in the VACS Index. Both the participant and review of medical records will be used as source of the data.

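### The Aim 3 marker–outcome association model does not name randomised arm, so a marker and an outcome that exercise moves separately can appear associated if both arms' follow-up or change data are analysed together

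*Combined protocol and SAP*

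**What the plan says.** Section 2.3.e (DNA Methylation, Aim 3) describes three things.

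- **Association model.** "To examine epigenetic association with each outcome, we will fit the linear regression model as follows". The displayed equation is missing from the text available to us, but its symbols are defined in words: a quantitative outcome Y, a candidate marker E, and Z, which is "the vector of covariates including age, race, smoking status and leukocyte proportions".
- **Arm comparison.** A separate sentence gives ANCOVA for the between-group difference over time. It is not described as a term of the association model.
- **Extension.** The association model is widened to cover batch/chip effects and "longitudinal measures using a linear mixed model". No arm or arm-by-time term is named.

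On multiplicity: "We will adjust the significance threshold for multiple testing using Bonferroni correction". The number of tests is not given. Table 7 lists the candidates as *NFKB2*, *ASC*, *GHRH*, *FGF1*, *EGF* and "5 CpG sites in genes related to CRP".

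Section 3.3.b (Inflammatory Biomarkers) says that pre/post cytokine changes "will be tested for association with changes in outcomes as well as between group differences". The sentence before it places cytokine change as a predictor in the models for the primary and secondary outcomes.

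**The concern.** The plan expects exercise to raise fitness and reduce sarcopenia, frailty and DNAm Age (Section 2.3.e). Aim 3 asks whether it also changes methylation and cytokines (Section 1.3). If exercise does both, participants in the exercise arm tend to have larger changes in the outcome and in the marker. A regression across both arms without an arm term then picks up the gap between the arms as a marker–outcome slope, even if people whose marker moves more do no better than others in the same arm.

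At stake is the mechanistic reading: a paper could report that methylation change tracks an outcome gain when the two share only the randomised treatment. Bonferroni controls the number of tests. It does not remove a bias that shifts the null value of each slope.

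**Working it through.** **What can be reproduced.** The plan states no figure for the association model. Its Aim 3 sample size of 34 is read from an outside simulation table and cannot be rebuilt without a methylation SD. As a check on the effect sizes used below, I recomputed the sample-size table with an exact paired t-test (two-sided 0.05, 80% power). DNAm Age (29/21/14) and chair stands (8/7/5) reproduce exactly. VO2peak comes out at 5/4/4 against the printed 4/3/2, and the step test at 12/9/7 against 16/14/9. These differences do not bear on this point.

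**Inputs**
- Number per arm: 40 (Section 3.1). With the 30% attrition in Section 3.3.a, 40 × 0.70 = 28.
- Outcome shift, low: DNAm Age 62 (10.8) to 68.7 (10), pre/post correlation 0.5. SD of change = √(10.8² + 10² − 2×0.5×10.8×10) = 10.42, and 6.7/10.42 = 0.64.
- Outcome shift, high: VO2peak 2.17 (0.13) to 2.46 (0.14), correlation 0.3. SD of change = √(0.13² + 0.14² − 2×0.3×0.13×0.14) = 0.160, and 0.29/0.160 = 1.81.
- Marker shift: **assumption**. A paired design with n=34 and 80% power at two-sided 0.05 implies about 0.50 SD. A shift of 1.0 is shown as the upper end.
- Thresholds: 0.05, and 0.005 for ten tests (**assumption**: one site in each of five genes plus five CRP-related sites, one outcome).
- Control-arm change 0 (**assumption**). True within-arm association 0.

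**Correlation produced by arm alone** (1:1 allocation, shifts dY and dE in SDs of change):

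r = 0.25·dY·dE / √[(1 + 0.25·dY²)(1 + 0.25·dE²)]

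- dY 0.64, dE 0.50: 0.080/√(1.102 × 1.0625) = 0.074
- dY 1.81, dE 0.50: 0.226/√(1.819 × 1.0625) = 0.163

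**Hand check by Fisher's z**, with z = atanh(r)·√(N−3). For r = 0.163 and N = 80, z = 0.164 × 8.77 = 1.44. The chance of passing 1.96 is P(Z > 0.52) = 30%, and of passing 2.81 is P(Z > 1.37) = 9%. For r = 0.074 and N = 56, z = 0.54, giving 8% and 1% (both tails).

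**Simulation, change-score model without arm** (six noise covariates, 4,000 runs per cell; false positives at 0.05 / 0.005):

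| dY, dE | 28 per arm | 40 per arm |
|---|---|---|
| 0.64, 0.50 | 8% / 1% | 10% / 2% |
| 1.81, 0.50 | 22% / 4% | 28% / 7% |
| 1.0, 1.0 | 30% / 8% | 41% / 13% |
| 1.81, 1.0 | 58% / 24% | 76% / 44% |

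Without the noise covariates, the 1.81/0.50 case at 40 per arm is about 31% and 8–9%. With arm in the model every cell is 4–6% at 0.05. If exercise does not move the outcome, the model without arm also stays near 5%.

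**Simulation, two-visit mixed model** (40 per arm, pre/post correlation 0.5, 1,000 runs per cell; false positives at 0.05):

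| dY, dE | Marker only | + time | + arm + time | + arm-by-time |
|---|---|---|---|---|
| 0, 0 | 6% | 6% | 6% | 6% |
| 0.64, 0.50 | 18% | 10% | 7% | 5% |
| 1.81, 0.50 | 52% | 33% | 19% | 7% |
| 1.0, 1.0 | 77% | 44% | 27% | 6% |

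An arm main effect does not repair the longitudinal version, because arm acts on the change and not on the average level.

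**The case against.** The best defence is that the flaw is inferred. The plan does not say that both arms are pooled. It does not say whether Y and E are baseline, follow-up or change values. Its covariate list is introduced as inclusive rather than complete, and the equation cannot be read here. With baseline values only, randomisation makes arm unrelated to both variables and the bias disappears. All of this stands as a limit on the claim. It does not remove the point: the model is extended to repeated measures, so follow-up data enter, and an open list does not pre-specify the one design variable that the model needs.

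Three stronger readings are tempting and are not supported.

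- *Any marker and outcome that exercise moves will appear associated.* With effects taken or inferred from the plan, a significant result is the minority outcome. Rates above one half in the change-score model need a marker shift near 1 SD, for which the documents give no basis. More than ten tests would lower the rates further. At an assumed 0.001 (fifty tests), the 1.81/0.50 case gives P(Z > 3.29 − 1.44) = 3% at 40 per arm, though nominal is 0.1%.
- *The cytokine analysis repeats the flaw.* Section 3.3.b puts cytokine change into outcome models that may already carry group, so the text is ambiguous rather than wrong.
- *Aim 3 as a whole is compromised.* Section 1.3 states Aim 3 as the effect of exercise on methylation and cytokines. Those are randomised comparisons, and this point does not touch them.

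**Conclusion.** The point holds in a limited form. The association model and its longitudinal extension name no arm term. If they are run as described on both arms' follow-up or change data, the slope is confounded by treatment.

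For change scores, the false-positive rate is about 8–31% at 0.05 and 1–9% at 0.005, against nominal rates with arm included. This rests on three assumptions: a marker shift of 0.5 SD, ten tests, and no change in controls. Larger marker shifts give higher rates; a shift of zero in either variable, or baseline-only data, gives none. The two-visit mixed model is more exposed: 18–52% at 0.05 for the same shifts when neither time nor arm is included.

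This should be corrected before analysis. It bears on the mechanistic interpretation and not on the trial's randomised conclusions.

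**What to change.** In Section 2.3.e, for the Aim 3 association model:

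1. State whether Y and E are baseline, follow-up or change values, and whether both arms enter.
2. Where they are change or follow-up values, name arm as a covariate.
3. In the longitudinal mixed model, name arm, time and arm-by-time; arm plus time is not enough. Alternatively, report the slope within each arm.
4. State the number of tests behind the Bonferroni threshold.

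In Section 3.3.b, confirm that the models using cytokine change as a predictor also carry arm, in the same form.

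The cost is one or two degrees of freedom and a few lines of text. No new data are needed, and the between-group ANCOVA does not change. Nothing in this check argues for a site term, so none is proposed.

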
sample size even with attrition as high as 40% and a correlation of within person values as low as 0.3.

AIM 2: Since change in DNAm

AIM	Dependent Variable	Pre/ Post Intervention		Sample Size		
		Pre-Mean (SD)	Post-Mean (SD)	correlation pre/post		
		0.3	0.5	0.7		
1	$\text{VO}_2\text{peak, L/min}$	2.17(0.13)	2.46(0.14)	4	3	2
	2-min. step test	67 (18)	86 (17)	16	14	9
	Chair stands ⁴⁶	17.8 (5.4)	25.4 (5.6)	8	7	5
2	DNAm Age, yrs ²³	62(10.8)	68.7(10)	29	21	14

Age with exercise training is unknown, we used values from our observational study of 19 male Veterans before and after antiretroviral therapy was started.²³ We will have adequate sample size even with attrition of 28% and a correlation of within person values as low as 0.3.

AIM 3: As summarized by Tsai and Bell, epigenetic data generated by EWAS have two additional factors that affect power, stability of CpG sites and their variance within a biological sample.⁴⁷ They performed power simulations based on micro-array based datasets (e.g., Illumina 450K) with the assumption that disease risk is affected by a single CpG site. Using Wilcoxon signed-rank test for paired study design (one sample), 80% power and $\alpha < 0.05$, they generated sample size estimates based on percent methylation difference (p.1437).⁴⁷ Denham reported a 11.6% methylation difference after 4 weeks of AEX in a single CpG site in the EGF gene, which also showed decreased mRNA expression.⁴⁸ On the basis of this literature, a sample size of 34 participants is sufficient to find an 11% difference in methylation of a relevant candidate gene with exercise.

2.3.f Data Sharing and Publication

Final data sets underlying all publications resulting from the proposed research will be shared outside the VA. A Limited Dataset (LDS) will be created and shared pursuant to a Data Use Agreement (DUA) appropriately limiting use of the dataset and prohibiting the recipient from identifying or re-identifying (or taking steps to identify or re-identify) any individual whose data are included in the dataset. Data sharing and preservation will enable validation of results and advancing science by broadening the value of research data for intra and inter disciplinary developments ultimately benefiting the scientific community, industry, and the public at large.

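### Aim 3 uses single-step Bonferroni where Holm's procedure gives the same family-wise control and is never less powerful; the gain is modest

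*Combined protocol and SAP*

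**What the plan says.** The Aim 3 paragraph of section 2.3.e describes three analyses: change in each candidate marker over 12 weeks, regression of outcomes on each marker, and ANCOVA for the between-group difference. It closes with one multiplicity rule: "We will adjust the significance threshold for multiple testing using Bonferroni correction", with the threshold written as 0.05 over the number of tests. No step-down method appears anywhere in the document.

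The number of tests is not given. The plan says "The candidate epigenetic markers will involve individual CpG sites previously identified and discussed in detail section D4c", and that section is not in the document available for review. Table 7 (section 3.3.b) gives a partial list: *NFKB2*, *ASC*, "5 CpG sites in genes related to CRP", *GHRH*, *FGF1* and *EGF*.

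The Aim 3 sample size rests on a paired Wilcoxon test at alpha 0.05 and 80% power for a single site, and concludes that "a sample size of 34 participants is sufficient to find an 11% difference in methylation of a relevant candidate gene with exercise". Section 3.1 says "Eligible participants will be randomized to exercise training (N=40) or control (N=40) groups". Section 3.3.a expects 30% attrition.

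**The concern.** A single-step rule applies the strictest threshold to every test, including those left after other hypotheses in the family have been rejected. Holm starts at the same threshold and relaxes it after each rejection, with no loss of family-wise control. For testing alone, Bonferroni therefore gives up some power and gets no extra error protection in return.

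At stake is the number of candidate sites that Aim 3 can declare changed. Power is scarce here because the arms are small and the threshold is divided over several sites. The validity of any Aim 3 conclusion is not in question.

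**Working it through.** **1. Why Holm cannot do worse.** Order the p-values p(1) ≤ … ≤ p(m). Holm compares p(i) with 0.05/(m − i + 1) and stops at the first failure. Every one of these thresholds is at least 0.05/m, so any test with p ≤ 0.05/m is also rejected by Holm. If m0 hypotheses are truly null, the first false rejection comes at step m − m0 + 1 or earlier, so that p-value is at most 0.05/m0. The union bound then gives family-wise error ≤ m0 × 0.05/m0 = 0.05 under any dependence. The first threshold is 0.05/m in both methods, so the chance of at least one rejection in the family is identical.

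**2. Inputs**
- m: not stated. Assumed 10 = *NFKB2* + *ASC* + 5 CRP-related sites + *GHRH* + *FGF1* + *EGF*, one site per named gene (Table 7). Range shown: 8 to 20.
- Per arm: 40 (section 3.1), or 40 × 0.70 = 28 after 30% attrition.
- Sidedness: not stated; two-sided assumed.
- Effect: the plan gives 11% but no SD, so 34 cannot be reproduced directly. It is back-solved in step 3.

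**3. Effect implied by the plan.** The noncentral-t method was first checked on the plan's DNAm Age row. At correlation 0.3 the SD of change is √(10.8² + 10² − 2 × 0.3 × 10.8 × 10) = √151.84 = 12.32, so dz = 6.7/12.32 = 0.544 and n = 29, as stated. The entries 21 and 14 also reproduce. Solving the same paired t-test for 80% power at n = 34 and alpha 0.05 gives dz = 0.495 (0.507 with a Wilcoxon efficiency of 0.955). The value 0.495 is used below.

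**4. Threshold.** 0.05/10 = 0.005. Family-wise error is at most 10 × 0.005 = 0.05 (0.0489 if independent), against 0.401 for ten independent tests with no correction.

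**5. Between-arm tests.** Assumptions: change-score t-tests, equal SD of change in both arms, no change in controls, independent markers. The noncentrality is dz × √(n/2).
- 28 per arm: 0.495 × √14 = 1.85, critical t(54) = 2.93, Bonferroni power about 15%.
- 40 per arm: 0.495 × √20 = 2.21, critical t(78) = 2.89, Bonferroni power about 26%.

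Holm's gain in average power per true marker, by simulation, in percentage points:

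| True markers of 10 | 28 per arm | 40 per arm |
|---|---|---|
| 3 | 0.3 | 0.7 |
| 5 | 0.6 | 1.4 |
| 8 | 1.1 | 2.7 |
| 10 | 1.5 | 3.8 |

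A second run of 200,000 replicates agreed to within 0.1 point. Holm's family-wise error stayed below 0.05, and no test was rejected by Bonferroni alone. The same simulation with m = 8 gives gains of 0.5 to 2.1 points with 3 to 5 true and 1.9 to 4.6 with all 8 true. With m = 20 it gives 0.1 to 0.4 and 0.7 to 2.1 (all 20 true).

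**6. Settings more favourable to Holm**
- Paired test, n = 34, m = 10: 46.1% to 47.6% (3 true), 46.4% to 49.8% (5 true), 46.3% to 57.8% (all 10 true). A correlation of 0.3 between markers gave nearly the same average power and error.
- z-tests with noncentrality 2.8 to 3.6 (Bonferroni power about 50-79%), all 10 true: gains of about 11 to 14 points.

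**7. What Holm leaves untouched.** For the paired test at n = 34, moving from 0.05 to 0.05/10 lowers power per marker from 80% to about 46% (50% at m = 8, 37% at m = 20). About 59 pairs (56 to 66) would be needed to regain 80%.

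**The case against.** The strongest reply is that this is a preference. Bonferroni is pre-specified, valid under any dependence, unbiased, and has simple simultaneous confidence intervals that Holm lacks. The probability of finding at least one marker is the same under both. All of this stands, and it is why the point is minor. It does not remove the fact that, for testing, Holm dominates at no cost in family-wise error.

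A second reply is that m = 10 is a guess. That also stands: sites per gene are not given, and Aim 3.1 concerns genes encoding pro-inflammatory cytokines, whereas Table 7 lists *GHRH*, *FGF1* and *EGF* separately as exercise-related. The ordering of the two methods does not depend on m. The size of the gain does, and it shrinks as m grows.

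Three stronger readings are tempting, and the documents do not support them.
- A reader might infer double-digit power gains. These need per-test power near 50-80% and all markers truly changing. No part of the plan supplies either, and the effect implied by its own 34 gives 15-26% between arms.
- A reader might infer that marker-outcome associations share the divisor with the between-arm tests and shrink the threshold much further. Section 2.3.e does not define the family, so this is possible but not stated.
- A reader might want to split Aim 3 into two Holm families at 0.05 each. That could raise Aim 3-wide error to about 0.05 + 0.05 = 0.10, so it would no longer be the same error control.

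**Conclusion.** The point holds as a minor, optional improvement. Holm over the same tests keeps family-wise error at 5% and is never less powerful than the planned rule. On the only effect size recoverable from the plan, with m = 10 and 28 to 40 per arm, the gain is about 0.3 to 1.4 points per true between-arm marker with 3 to 5 true, and 1.5 to 3.8 points with all 10 true.

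These figures assume two-sided change-score t-tests, independent markers, equal SD of change, no change in controls, and one site per named gene. ANCOVA could do somewhat better. It should not be read as a flaw in the validity of Aim 3, nor as a remedy for a sample size set at an unadjusted 0.05 for one site.

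**What to change.** In section 2.3.e, keep whatever family of tests the plan intends and replace the Bonferroni sentence with: *Multiplicity will be handled by Holm's step-down procedure at two-sided family-wise 0.05 over the same tests.* Report Holm-adjusted p-values beside unadjusted 95% confidence intervals, labelled as unadjusted.

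The cost is SAP wording only, with no added data, participants or procedures. The small downside is that matching simultaneous intervals are less simple under Holm, and an unadjusted interval can exclude zero where the adjusted p-value is not significant, so the label is needed. Either method requires the tests to be counted. Writing out that list is a separate task, and so is revisiting the Aim 3 sample size at the adjusted alpha.
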